9.1.1 Inclusion Criteria

Participants must meet ALL of the following inclusion criteria to be eligible for participation in the study:

- 1. At least 18 years of age
- 2. Scheduled to undergo elective laparoscopic procedure

CP008 Revision: A Date: 13Sep2022	CONFIDENTIAL	Page 18 of 41

3. Willing and able to provide a written Informed Consent Form (ICF) to participate in the study prior to any study required procedures

9.1.2 Exclusion Criteria

Individuals must be EXCLUDED from participation in this study if ANY of the following exclusion criteria are met:

- 1. Individuals with pacemakers, defibrillators, or other electromedical implants
- 2. Individuals with ferromagnetic implants
- 3. Individuals with significant comorbidities: cardiovascular, neuromuscular, chronic obstructive pulmonary disease, and urological disease (renal failure)
- 4. Individuals with clinical history of impaired coagulation confirmed by abnormal blood tests
- 5. Anatomical abnormality or disease of intended target tissue noted after initiation of index procedure that would prevent device use
- 6. The individual is pregnant or wishes to become pregnant during the length of study participation
- 7. Individual is not likely to comply with the follow-up evaluation schedule
- 8. Is participating in a clinical trial of another investigational drug or device
- 9. Is a prisoner or under incarceration

9.2 Screening/Baseline Evaluation

Patients will be prescreened for eligibility and if qualified will be approached with the study information and asked if they are willing to participate. The Screening visit will occur within 30 days prior to the laparoscopic procedure.

Informed consent will be obtained per Section 13.3. All patients who sign a consent form are considered study subjects. A study participant is considered enrolled after they have signed an informed consent form and after the inclusion/exclusion criteria have been met.

The following evaluations are required at the time of subject screening /baseline:

- Demographic Information: gender, race, age, weight, and height, and smoking status
- Medical / Surgical History
- Pre-operative blood draw for determination of coagulation disorders if warranted
- Urine pregnancy test for women of childbearing potential. Note that if the screening test is more than 1 week prior to the index

procedure, a second urine pregnancy test is required within 7 days of the index procedure.

9.3 Procedure

The Investigator will perform the surgical procedure in accordance with the methods detailed in the Instructions for Use (IFU).

The following intra-operative data will be collected:

- General anesthesia time
- Operative time (from the first incision to the last suture's placement)
- Device and procedure observations
- Number of required surgeons
- Conversion to open surgical procedure
- The need for an additional surgical tool to mobilize the intended organ or tissue
- Estimated blood loss
- Video recording of the overall procedure
- Adverse events

9.4 Post-Procedure / Hospital Discharge

Before hospital discharge the following data will be collected:

- Length of hospital stay (time from admittance to post-anesthesia care unit until hospital discharge)
- Length of time spent in Post Anesthesia Care Unit (PACU)
- Adverse events, if any

9.5 Follow-up

All subjects will be asked to return to the investigational site at 7 days and again at 30 days post-procedure according to the study schedule described in Table 1: Schedule of Assessments. Subjects will be queried about adverse events at these study visits. Study visits should be scheduled as closely as possible to the earlier part of the time period to allow for rescheduling if needed due to last minute schedule changes. Visits not completed within the specified time period will be regarded as deviations.

9.6 Unplanned Follow-up Visits

Subjects returning for unscheduled visits will be reported on the Unscheduled Visit case report form.

9.7 Early Discontinuation / Withdrawal

All subjects will be informed of their right to withdraw from the clinical study at any time without penalty or loss of benefits to which the subject is otherwise entitled. Additionally, the Investigator may prematurely discontinue any

CP008 Revision: A Date: 13Sep2022	CONFIDENTIAL	Page 20 of 41

subject's participation in the study if the Investigator feels that the subject can no longer fully comply with the requirements of the study or if any of the study procedures are deemed potentially harmful to the subject. The reason for early discontinuation will be documented in the source documents and the Study Termination case report form.

9.8 Lost to Follow-up Subjects

Every attempt will be made to have all subjects complete the follow-up visit schedule. A subject will not be considered lost to follow-up unless efforts to obtain compliance are unsuccessful. At a minimum, the effort to obtain follow-up information will include three attempts to make contact via telephone or email and if unsuccessful, then a certified letter from the Investigator will be sent to the subject's last known address. In general, the study Site Coordinator should attempt to contact the subject as soon as possible after each missed visit to reschedule the visit.

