10.3 Minimization of Risk and Monitoring Procedures

Levita Magnetics has attempted to mitigate risks as much as possible through product design and development of the MSS which included *in vivo* performance testing, human factors testing, non-clinical performance testing, clinical testing of the MSS in other surgical procedures, biocompatibility testing, sterilization validation, reprocessing validation and shelf-life validation. Additionally, careful labeling, IFU and training are provided as detailed below for the MSS and DRAA.

Risks will be further mitigated through selection of qualified physicians with competence in minimally invasive surgery, appropriate training, and study monitoring.

CP008 Revision: A Date: 13Sep2022	CONFIDENTIAL	Page 22 of 41

Investigators who participate in the study will be experienced and skilled in laparoscopic surgical techniques. Additionally, Investigators, in conjunction with the investigational site, will have adequate resources for participation in a clinical study.

The study has been designed to ensure treatment and follow-up of subjects are consistent with current medical practice.

Each Investigator will ensure oversight and approval of the study by the Ethics Committee (EC) prior to initiation of the clinical study at his/her investigational site.

The Investigator and study personnel will be trained on the clinical protocol. All Investigators who have not previously used the Levita MSS will undergo training with MSS prior to first use during the clinical study.

All Investigators and operating room support personnel will be provided with a detailed IFU during training and as a reference for review as needed.

The IFU details appropriate safety zones for use of the Magnetic Controller in an OR setting and considerations for users of a product with a strong magnet.

Study personnel are also trained with and receive a "Magnetic Surgery Screening Checklist" and Operating Room (OR) signage to ensure safe use of the system for subjects and users.

Subjects will be carefully evaluated against the inclusion/exclusion criteria prior to entering the clinical study to ensure that their diagnosis and medical status are appropriate for participation in the clinical study.

Subjects will be monitored up to the 30-day follow-up visit as defined in the study protocol. The follow-up visit will be with an Investigator to monitor the subjects' status.

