A study Investigator will evaluate the subject for any adverse events potentially related to the device.

Levita Magnetics or its designee may conduct monitoring visits at the investigative sites at the initiation of the study and periodically throughout the study to evaluate protocol compliance and to determine if there are any issues that may affect the safety or welfare of the subjects.

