11.6 Handling Missing Data

Only subjects with non-missing data for safety will be used.

CP008 Revision: A Date: 13Sep2022	CONFIDENTIAL	Page 24 of 41

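### Section 9.8 does not require adverse event status to be asked and recorded when a subject who missed a visit is reached, and 11.6 leaves that subject's place in the safety summary open

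*Combined protocol and SAP*

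**What the plan says.** **Where post-discharge AEs are collected.** Section 9.5: "All subjects will be asked to return to the investigational site at 7 days and again at 30 days post-procedure", and "Subjects will be queried about adverse events at these study visits". In Table 1 the AE row is the only one ticked at days 7 and 30. Section 14.1.1 likewise ties AE assessment and documentation to the procedure and the follow-up visits. Section 10.3 adds an Investigator's assessment: "The follow-up visit will be with an Investigator to monitor the subjects' status", and "A study Investigator will evaluate the subject for any adverse events potentially related to the device".

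**What happens after a missed visit.** Section 9.8 makes three statements:
- On status: "A subject will not be considered lost to follow-up unless efforts to obtain compliance are unsuccessful".
- On the minimum effort: "the effort to obtain follow-up information will include three attempts to make contact via telephone or email", followed by a certified letter if these fail.
- On the usual practice: "the study Site Coordinator should attempt to contact the subject as soon as possible after each missed visit to reschedule the visit".

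**How missing data are handled.** Section 11.6: "Only subjects with non-missing data for safety will be used". The protocol does not define what counts as non-missing. Section 11.4 reports all AEs in a safety population, which is also undefined.

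**What is collected regardless.** Sections 9.3 and 9.4 collect AEs during the operation and before discharge. Section 14.2 requires any AE arising during the study to be reported.

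**The concern.** After discharge, the plan learns of AEs mainly by asking the subject in person, twice. When a subject does not come, the plan requires contact but does not require the AE question to be put or the answer recorded. A subject who answers the telephone but will not travel has no stated next step. Up to three sites could handle the same call differently.

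Non-return after surgery may well be related to outcome. A subject may stay away because of feeling well, or because of being admitted elsewhere. The missing AE data may therefore not be a random subset, and the direction of the error cannot be known in advance.

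Safety is one of the two parts of the study objective, and there are at most 50 subjects, so a few unknown outcomes visibly change what can be said. The undefined wording of 11.6 adds a second risk: an AE already observed at operation or discharge could leave the summary because a later visit was missed.

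**Working it through.** The plan contests no figure here. Section 11.2 gives 50 subjects without a formula, and no dropout rate is stated, so there is nothing to reproduce. The check is first of the text, then an illustration on stated assumptions.

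**Step 1. Does any section supply the missing instruction?**

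| Section | What it covers | Closes the gap? |
|---|---|---|
| 9.5, Table 1 | AE query at on-site visits, days 7 and 30 | No; it depends on attendance |
| 9.6 | Form for subjects who return unscheduled | No; it depends on attendance |
| 9.7 | Reason for discontinuation is documented | No; no closing AE query |
| 9.8 | Contact for follow-up information and to rebook | Permits an AE query, does not require or record one |
| 14.1.1 | AEs documented at procedure and follow-up visits | No; it depends on attendance |
| 14.2, 14.5 | Any AE, and any death, is reported | Only once the site knows of it |

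No section orders a telephone AE query or a hospital-record check.

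**Step 2. How much could unknown subjects matter?** Assumptions: 5 of 50 (10%) miss the final visit; 2 of the remaining 45 have a device-related event; the 5 have unknown status.
- Reported rate: 2/45 = 4.4%, exact (Clopper-Pearson) 95% CI 0.5% to 15.1%.
- Lower extreme, none of the 5 had an event: 2/50 = 4.0%.
- Upper extreme, all 5 did: (2 + 5)/50 = 7/50 = 14.0%.
- Width of the range: 14.0 − 4.0 = 10 points, which is 5/50.
- Each subject whose AE status is settled by telephone removes 1/50 = 2 points. A report of no event lowers the upper bound; a report of an event raises the lower bound.
- A record check settles only readmission, reoperation and death. It cannot rule out a non-serious AE, so it does not remove the full 2 points.

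**Step 3. What if 11.6 removes subjects with observed AEs?** Assumption: 5 of 50 treated subjects have an AE (5/50 = 10.0%) and 5 subjects are dropped for a missed visit.

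| Dropped subjects who had an AE | Reported rate |
|---|---|
| 0 | 5/45 = 11.1% |
| 1 | 4/45 = 8.9% |
| 2 | 3/45 = 6.7% |

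**Step 4. Is loss of precision the issue?** With zero events the one-sided 95% upper bound is 1 − 0.05^(1/n):

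| Assumed loss | n | Upper bound |
|---|---|---|
| 0% | 50 | 5.8% |
| 4% | 48 | 6.1% |
| 10% | 45 | 6.4% |
| 20% | 40 | 7.2% |

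The loss of precision is modest. The issue is unknown status and the possible discarding of observed events.

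**The case against.** The best defence is that 9.8 already gives the telephone and email attempts an information-gathering purpose, and that the rebooking sentence is softer and comes second. A reader who sees only that later sentence might infer that staff telephone solely to rebook. The text does not support that: asking about AEs on the call is permitted. What stands is that the question is neither required nor given a place on the case report form.

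Three other strong readings also fail:
- *A non-attender yields no safety data.* Intra-operative and discharge AEs are already collected, and 14.2 makes reportable any AE the site learns of, including one mentioned on a rebooking call. Only events after the last attended visit that the site does not otherwise learn of are at risk.
- *Section 11.6 drops the subject.* That is one reading of an undefined phrase. A subject with procedure and discharge data may qualify, and 11.4 reports all AEs in the safety population.
- *A reached subject is handled like one never reached.* The certified letter follows only failed contact, so the two paths do differ. What is missing is the next step for a reached subject who declines to attend.

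It is also fair to say that the visit is more than an AE questionnaire. Section 10.3 has an Investigator see the subject, so giving priority to rebooking is defensible and a call by staff is not a full substitute. Finally, section 11.1 presents the study as descriptive, with no hypothesis or safety threshold, and the 14% bound requires all five missing subjects to have had an undetected device-related event. These arguments limit the size of the problem. They do not supply the missing instruction.

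**Conclusion.** The gap is real but narrow. The plan requires contact after a missed visit, yet does not require AE status to be asked and recorded on it, and no section orders a record check. Post-discharge AEs in subjects who do not attend can go unascertained, and 11.6 leaves unclear whether those subjects, and AEs already observed in them, stay in the safety summary.

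The size depends on a dropout rate that the plan does not give. At an assumed 10% loss, a reported 4.4% is compatible with anything from 4% to 14%; the upper end is an extreme, not an expectation. Under the strict reading of 11.6, an assumed 10.0% AE rate could be reported as anything from 6.7% to 11.1% when up to two of five dropped subjects had an AE. This does not undermine the study. It is an inexpensive improvement in completeness for a stated objective, and worth making.

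**What to change.** **Section 9.8.** Add text to this effect: *At the first successful contact after a missed visit, site staff complete the adverse event query by telephone on the visit case report form (mode = telephone), for Investigator review, while still trying to rebook the visit. If no contact is made, the site checks the hospital records available to it for readmission, reoperation and death through day 30.*

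**Sections 11.4 and 11.6.** State that every treated subject and every observed AE stays in the safety summary. Report, for day 7 and day 30 separately, how many subjects were assessed on site, by telephone, by record only (serious outcomes only), or not at all.

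**Cost.** A few minutes on calls that the protocol already requires, one field on the form, and a record check for the few subjects not reached. No extra visits or staff are needed. Telephone reports are less detailed than an Investigator visit, which is why the mode is shown. A check of the site's available records can miss an admission elsewhere, so subjects assessed by record only should not be counted as having full AE status.

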9.9 Study Exit

Subjects will be considered to have completed and exited the study after the 30 day follow up visit has been completed.

9.10 Study Schedule of Assessments

Table 1: Schedule of Assessments

	Time Frame			
Assessment	Pre-op	Index Procedure & Discharge	7-day follow- up	30-day follow-up
Visit Window	- 30 days	NA	(± 3 days)	(± 7 days)
Informed Consent	√			
Medical History				
Demographics				
Blood Tests	$\sqrt{}$			
Pregnancy Test *	$\sqrt{}$	V		
Intra-operative assessments		V		
Adverse events		$\sqrt{}$	V	$\sqrt{}$

^{*} Urine pregnancy test for all women of childbearing potential at pre-op visit and repeated within 7 days of index procedure unless pre-op visit/prior urine pregnancy test was within 7 days of index procedure.

CP008 Revision: A Date: 13Sep2022	CONFIDENTIAL	Page 21 of 41		
This document contains proprietary and confidential information of Levita Magnetics.				
Do not copy, distribute, or share with others without prior written authorization from Levita Magnetics.				

10 RISK / BENEFIT ANALYSIS

10.1 Benefits

Possible benefits of the use of the Levita Magnetic Surgical System and Robotic Platform are a reduction in the number of surgical incisions needed to perform the surgery, with associated reduction in post-operative pain and scaring, a shorter length of stay in the hospital, faster recovery, and reduced intraoperative labor required.

10.2 Risks

There are risks associated with use of the Levita Magnetic Surgical System and Robotic Platform including:

- Electromagnetic field incompatibility or interference
- Malfunctioning of the device
- · Breakage of the device
- Allergic reaction related to the device
- Abdominal wall/cavity/tissue and/or organ injury or damage (e.g., inflammation, redness)
- Infection
- Tissue damage, including hematoma, bleeding or petechiae
- Vascular injury
- Gastro-intestinal injury
- Organ perforation
- Need for extended surgery
- Additional surgical intervention due to any of the above factors (includes reoperation)

These adverse events do not include all adverse events, which occur with surgery in general, but are important considerations particular to laparoscopic instrumentation.

10.3 Minimization of Risk and Monitoring Procedures

Levita Magnetics has attempted to mitigate risks as much as possible through product design and development of the MSS which included *in vivo* performance testing, human factors testing, non-clinical performance testing, clinical testing of the MSS in other surgical procedures, biocompatibility testing, sterilization validation, reprocessing validation and shelf-life validation. Additionally, careful labeling, IFU and training are provided as detailed below for the MSS and DRAA.

Risks will be further mitigated through selection of qualified physicians with competence in minimally invasive surgery, appropriate training, and study monitoring.

CP008 Revision: A Date: 13Sep2022	CONFIDENTIAL	Page 22 of 41

Investigators who participate in the study will be experienced and skilled in laparoscopic surgical techniques. Additionally, Investigators, in conjunction with the investigational site, will have adequate resources for participation in a clinical study.

The study has been designed to ensure treatment and follow-up of subjects are consistent with current medical practice.

Each Investigator will ensure oversight and approval of the study by the Ethics Committee (EC) prior to initiation of the clinical study at his/her investigational site.

The Investigator and study personnel will be trained on the clinical protocol. All Investigators who have not previously used the Levita MSS will undergo training with MSS prior to first use during the clinical study.

All Investigators and operating room support personnel will be provided with a detailed IFU during training and as a reference for review as needed.

The IFU details appropriate safety zones for use of the Magnetic Controller in an OR setting and considerations for users of a product with a strong magnet.

Study personnel are also trained with and receive a "Magnetic Surgery Screening Checklist" and Operating Room (OR) signage to ensure safe use of the system for subjects and users.

Subjects will be carefully evaluated against the inclusion/exclusion criteria prior to entering the clinical study to ensure that their diagnosis and medical status are appropriate for participation in the clinical study.

Subjects will be monitored up to the 30-day follow-up visit as defined in the study protocol. The follow-up visit will be with an Investigator to monitor the subjects' status.

A study Investigator will evaluate the subject for any adverse events potentially related to the device.

Levita Magnetics or its designee may conduct monitoring visits at the investigative sites at the initiation of the study and periodically throughout the study to evaluate protocol compliance and to determine if there are any issues that may affect the safety or welfare of the subjects.

11 STATISTICAL ANALYSIS

11.1 Statistical Methods

This study is not planned to provide statistical data but to provide initial outcomes for safety and feasibility of the DRAA used with the MSS.

Descriptive tables may be produced for baseline characteristics including demographics and medical history and for study outcomes.

11.2 Sample Size Justification

This is a single-arm, multi-center, investigational study to understand the safety and feasibility of the use of the DRAA with the MSS. A sample size of 50 subjects was planned to allow use of the system in a number surgeons and a number of different types of laparoscopic procedures. It is expected that enrollment of 50 subjects will provide appropriate information regarding the safety and feasibility of the DRAA and MSS in laparoscopic procedures.

11.3 Safety Variables

Safety will be monitored via the reported Adverse Events, in this study. All adverse events will be captured and reported. Adverse events will be summarized by relatedness to the device and/or procedure, seriousness, and level of severity. If device related, AEs will be further characterized as to relationship to the MSS the DRAA or both.

11.4 Safety

All adverse events for participants in the safety population will be reported.

- Serious Adverse Events
- Non-serious Adverse Events Device Related Adverse Event
- Device Related Serious Adverse Events

Results will include the number of participants experiencing each type of event as well as the number of events.

11.5 Demographics

Subject demographics will be summarized using descriptive statistics (mean, median, Standard Deviation (SD), minimum, maximum), number of subjects for continuous variables (e.g., age), and frequency distributions (number and percentage of subjects) for categorical variables (e.g., sex at birth, race, and ethnicity).

